# **Evaluation of the Effect of Three Types of Rapid Maxillary Expanders (Conventional, Hybrid and MSE)**

**NCT05446714**

**Date of the document:14/5/2024**

### **Statistical analysis**

Data management and statistical analysis were performed using the Statistical Package for Social Sciences (SPSS) version 20. Data were explored for normality by checking the data distribution and using Kolmogorov-Smirnov and Shapiro-Wilk tests. Comparisons of normally distributed numeric variables between groups was performed by ANOVA test followed by Bonferroni post hoc test whenever a significance difference was detected. Pre and post values was compared by paired t test.

The mean difference was calculated by the formula:(Value after-value before)

Difference data were non-parametric and were compared between groups using Kruskal Wallis test.

All p-values are two-sided. P-values  $\leq 0.05$  were considered significant.

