## II- Outcomes

### I- Comparison between Hybrid and conventional hyrax groups

- **Molar distance:** There was no significant difference between groups in pre values ( $p= 0.094$ ). Regarding post treatment, The mean value recorded in Hybrid hyrax ( $52.21\pm2.59$ ) was significantly higher than that recorded in Butterfly hyrax ( $49.43\pm2.41$ ) ( $p= .016$ ). Moreover, there was a statistically significant difference between groups regarding the amount of change (difference) by treatment ( $p=0.000$ ), with the highest value recorded in MSE ( $8.88\pm1.58$ ), followed by Hybrid hyrax ( $7.24\pm1.77$ ) and the lowest value recorded in Butterfly hyrax ( $5.88 \pm 1.39$ ), (Table1, Fig.1, 11).
- **Premolar distance:** There was no significant difference between groups in pre values ( $p= 0.058$ ). Regarding post treatment, The mean value recorded in Butterfly hyrax ( $43.67\pm2.55$ ) and Hybrid hyrax ( $42.73\pm2.7$ ) was significantly higher than that recorded in MSE ( $38.46 \pm2.61$ ), ( $p= .000$ ). Moreover, the mean value of amount of change (difference) recorded in Butterfly hyrax ( $6.68\pm1.83$ ) and Hybrid hyrax ( $6.08\pm1.84$ ) was significantly higher than that recorded in MSE ( $4.43 \pm1.82$ ), ( $p= .005$ ). (Table1, Fig.1, 11).
- **Molar rotation:** There was no significant difference between groups, regarding pre and post values ( $p= 0.175$ ;  $p=0.207$  respectively in right side and  $p=0.06$ ;  $p=0.07$  in left side). There was no significant difference between groups regarding the amount of change (difference) by treatment ( $p=0.503$  in right side and  $p=0.757$  in left side), (Table 1, Fig 2,12)
- **Premolar rotation:** there was no significant difference between groups, regarding pre and post values for the right side ( $p= .566$ ;  $p=.609$  respectively) and the left side ( $p=.455$ ;  $p=.283$  respectively). Moreover, there was no statistically significant difference between groups regarding the amount of change (difference) by treatment in the right side and left sides ( $p=0.084$ ;  $p= .410$  respectively), (Table 1, Fig.3,12)

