- **Nasal floor molar:** There was no significant difference between groups in pre values ( $p= 0.058$ ) and post value ( $p=0.397$ ). There was a statistically significant difference between groups regarding the amount of change (difference) by treatment ( $p=0.000$ ), with the highest value recorded in MSE ( $4.38\pm0.85$ ), followed by Hybrid hyrax ( $2.6\pm1.04$ ) and the lowest value recorded in Butterfly hyrax ( $2.2\pm 1.49$ ), (Table 2, Fig.4, 13).
- **Nasal floor premolar:** There was no significant difference between groups in pre values ( $p= 0.701$ ). Regarding post treatment value, there was a statistically significant difference between groups ( $p=0.001$ ), with the highest value recorded in MSE ( $39.73\pm2.27$ ), followed by Hybrid hyrax ( $38.63\pm1.77$ ) and the lowest value

recorded in Butterfly hyrax ( $37.04 \pm 1.17$ ). Moreover, regarding the amount of change (difference) by there was a statistically significant difference between groups ( $p=0.000$ ), with the highest value recorded in MSE ( $4.87 \pm 0.62$ ), followed by Hybrid hyrax ( $3.43 \pm 0.74$ ) and the lowest value recorded in Butterfly hyrax ( $2.47 \pm 1.02$ ), (Table 2, Fig.4, 13).

- **Hard palate maxillary width 6:** There was no significant difference between groups in pre values ( $p= 0.083$ ). Regarding post treatment, the mean value recorded in MSE ( $64.31 \pm 1.8$ ) was not significantly different from butterfly Hyrax ( $63.59 \pm 2.15$ ), but was significantly higher than that recorded in Hybrid hyrax ( $62.04 \pm 2.68$ ), ( $p= .023$ ). The mean value of amount of change (difference) recorded in MSE ( $5.91 \pm 0.92$ ) was significantly higher than that recorded in Butterfly hydrax ( $3.37 \pm 0.96$ ) and Hybrid hyrax ( $3.17 \pm 1.54$ ), ( $p= .000$ ). (Table 2, Fig. 5, 14).
- **Hard palate maxillary width 4:** There was no significant difference between groups in pre values ( $p= 0.677$ ). Regarding post treatment, the mean value recorded in MSE ( $40.34 \pm 1.56$ ) was significantly higher than that recorded in butterfly hyrax ( $38.17 \pm 1.76$ ), ( $p= .002$ ). The mean value of amount of change (difference) recorded in MSE ( $6.35 \pm 1.25$ ) was significantly higher than that recorded in Butterfly hydrax ( $4.51 \pm 1.28$ ) and Hybrid hyrax ( $5.09 \pm 1.16$ ), ( $p= .001$ ). (Table 2, Fig. 5, 14).

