- **Molar inclination:** There was no significant difference between groups, regarding pre and post values ( $p= 0.353$ ;  $p=0.734$  respectively in right side and  $p=0.312$ ;  $p=0.892$  in left side). The mean value of amount of change (difference) recorded in MSE was significantly higher than that recorded in Butterfly hydrax and Hybrid hyrax, ( $p= .000$  in right side and  $p=0.003$  in left side). (Table 2, Fig 6, 15)
- **Premolar inclination:** There was no significant difference between groups, regarding pre values ( $p= 0.191$  in right side and  $p=0.355$  in left side). Post treatment, the mean value recorded in Butterfly hyrax was significantly higher than the other groups ( $p=0.003$  in right side and  $p=0.000$  in left side). The mean value of amount of change (difference) recorded in MSE was significantly higher than that recorded in Butterfly hydrax and Hybrid hyrax, ( $p= .000$  in right side and  $p=0.000$  in left side). (Table 2, Fig 7, 15)
- **Arch depth:** There was no significant difference between groups, regarding pre values ( $p= 0.064$ ). Post treatment, the mean value recorded in MSE was significantly lower than the other groups ( $p=0.007$ ). The mean value of amount of change (decrease) recorded in MSE was significantly greater than that recorded in Butterfly hydrax and Hybrid hyrax, ( $p= .000$ ), (Table 3, Fig 8, 16)

- **Incisor inclination:** There was no significant difference between groups, regarding pre and post values ( $p= 0.243$  and  $p=0.922$  respectively). The mean value of amount of change (decrease) recorded in MSE was significantly greater than that recorded in Butterfly hydrax and Hybrid hyrax, ( $p= .001$ ), (Table 3, Fig 9, 18)
- **Anterior suture opening:** There was no significant difference between groups, regarding pre values ( $p= 0.290$ ). The mean value recorded in MSE post treatment was significantly higher than that recorded in Butterfly hydrax and Hybrid hyrax, ( $p= .000$ ). The mean value of amount of change (increase) recorded in MSE was significantly higher than that recorded in Butterfly hydrax and Hybrid hyrax, ( $p= .001$ ), (Table 3, Fig 10, 18)

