## II-Comparison between pre and post values Hybrid and conventional hydrax groups

Comparing the pre and post values revealed that the post treatment value was significantly higher in post value compared to the pre value in molar and premolar distance (Fig.1), right and left molar rotation (Fig.2), right and left premolar rotation (Fig.3), nasal floor first premolar and molar (Fig.4), hard palate maxillary width first molar and premolar (Fig.5), right and left molar inclination (Fig.6), right and left premolar inclination (Fig.7) and anterior and posterior suture opening (Fig.10). On the other hand, Arch depth and incisor inclination recorded significantly lower post value compared to the pre value (Fig. 8,9), (Table 1-3)

Table (1) Descriptive statistics and comparison between (ANOVA test) and within group (i.e. between pre and post value) (paired t test) regarding molar and premolar distance; molar and premolar rotation right and left

GROUP	Pre		Post		Amount of change (post-pre)			P Within group	
	Mean	Std. Dev	Mean	Std. Dev	Mean	Std. Dev	Median		
Molar distance	Butterfly hyrax	43.55	1.97	49.43 b	2.41	5.88 c	1.39	5.77	.000*
	Hybrid hyrax	44.79	4.27	52.21 a	2.59	7.42 b	1.77	7.50	.000*
	MSE	42.14	3.25	51.01 ab	2.56	8.88 a	1.58	8.95	.000*
	P value bet. groups	.094ns		.016*		.000*			
Premolar distance	Butterfly hyrax	36.99	4.60	43.67 a	2.55	6.68 a	1.83	6.20	.004*
	Hybrid hyrax	36.65	3.15	42.73 a	2.70	6.08 a	1.84	5.90	.002*
	MSE	34.03	3.12	38.46 b	2.61	4.43 b	1.82	4.85	.002*
	P value bet. groups	.058 ns		.000*		.005*			
Molar rotation right	Butterfly hyrax	58.32	4.68	59.57	4.74	1.25	.67	1.10	.000*
	Hybrid hyrax	61.50	4.54	62.54	4.42	1.04	.58	1.10	.000*
	MSE	61.95	7.38	62.99	7.26	1.04	.65	0.90	.000*
	P value bet. groups	.175ns		.207 ns		.503 ns			
Molar rotation left	Butterfly hyrax	59.75	5.31	61.17	5.27	1.42	.51	1.50	.000*
	Hybrid hyrax	64.31	5.57	65.55	5.46	1.25	.82	1.10	.000*
	MSE	60.43	5.65	61.90	5.54	1.48	1.06	1.20	.000*
	P value bet. groups	.060 ns		.070 ns		.757 ns			
Premolar rotation right	Butterfly hyrax	74.71	6.68	75.84	6.64	1.13	.40	1.10	.000*
	Hybrid hyrax	73.79	6.58	74.71	6.48	.93	.48	0.90	.000*
	MSE	76.43	7.60	77.21	7.60	.78	.42	0.75	.000*
	P value bet. groups	.566 ns		.609 ns		.084ns			
Premolar rotation left	Butterfly hyrax	74.23	6.40	75.27	6.33	1.05	.32	1.10	.000*

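### Groups are compared on raw post values and raw change with no adjustment for the pre value; several post 'no difference' results reflect this, and MSE over Hybrid on molar distance is uncertain

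*SAP*

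**What the plan says.** The SAP's Statistical analysis section gives two between-group comparisons. For values at each time, "Comparisons of normally distributed numeric variables between groups was performed by ANOVA test followed by Bonferroni post hoc test". For post minus pre, "Difference data were non-parametric and were compared between groups using Kruskal Wallis test". No covariate appears in the SAP or the protocol, no pairwise test is named to follow Kruskal-Wallis, and neither comparison is given precedence. The outcome tables still print pairwise letters on the change column, and their captions name only ANOVA and the paired t test: "Descriptive statistics and comparison between (ANOVA test) and within group (i.e. between pre and post value) (paired t test".

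The results text then reports both comparisons for most outcomes. For molar inclination and again for incisor inclination it says "There was no significant difference between groups, regarding pre and post values", next to a significant result on change. For hard palate width 6 it says that MSE on post values "was not significantly different from butterfly Hyrax", while on change MSE is reported above both other arms. For molar distance the text gives the order of change as "with the highest value recorded in MSE ( $8.88\pm1.58$ ), followed by Hybrid hyrax ( $7.24\pm1.77" and Butterfly last; outcome Table 1 gives MSE and Hybrid different letters on change.

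**The concern.** When pre and post values correlate strongly, a comparison of raw post values carries nearly all the between-patient spread and any chance imbalance at the start. Raw change removes the spread but implicitly fixes the slope of post on pre at 1. Adjusting for the pre value estimates that slope. Since the arms were randomised, neither raw comparison is biased; what is at stake is precision and two competing answers for one outcome.

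With no rule for which comparison decides, a reader can quote the post result as a finding of no difference where the change result says otherwise. Conversely, where the slope is well below 1 and the arms start apart, raw change over-corrects, and a pairwise claim on change may depend on the method.

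**Working it through.** **Inputs.** Means and SDs for pre, post and change come from outcome Tables 1-3; n = 15/15/16 (Butterfly/Hybrid/MSE) from the demographic tables. Incisor change means are taken as post minus pre because the table cells are broken.

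**Reproducing the SAP.** One-way ANOVA on post values from the printed summaries gives p = .734, .890, .991, .022 and .016 for right molar, left molar and incisor inclination, hard palate width 6 and molar distance. The tables print .734, .892, .992, .023 and .016. The Kruskal-Wallis results need patient data and cannot be reproduced.

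**Rows left out.** A change SD cannot be smaller than |SDpre - SDpost|. Butterfly breaks this for premolar distance (1.83 against 2.05), nasal floor molar (1.49 against 3.40) and arch depth (0.38 against 0.40; 0.385 against 0.39 allowing for rounding). The left premolar inclination change SDs repeat the means, and posterior suture opening has no baseline variation. That leaves 13 of 18 measures.

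**Method.** Within-arm covariance = (SDpre² + SDpost² - SDchange²)/2. Pool over arms with weights n-1 to get Sxx, Sxy and Syy. Slope b = Sxy/Sxx; residual mean square = (Syy - Sxy²/Sxx)/42; adjusted difference = post difference - b × pre difference; SE² = residual mean square × (1/n1 + 1/n2 + (pre difference)²/Sxx). The Bonferroni multiplier for three pairs on 42 df is 2.494.

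**Worked example: hard palate width 6, MSE minus Butterfly.**
- Covariances: Butterfly (6.200 + 4.623 - 2.372)/2 = 4.226; likewise Hybrid 7.600 and MSE 4.174.
- Sxx = 301.27, Sxy = 228.17, Syy = 213.87, so b = 0.7574 and the residual mean square is 0.978.
- Adjusted difference = (64.31 - 63.59) - 0.7574 × (58.39 - 60.43) = 0.72 + 1.545 = 2.27.
- SE = √[0.978 × (1/16 + 1/15 + 2.04²/301.27)] = 0.374; interval 2.27 ± 2.494 × 0.374 = 1.33 to 3.20.

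**Results (Bonferroni 95% CI).**

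| Comparison | Raw post | ANCOVA | Raw change |
|---|---|---|---|
| Right molar inclination, MSE-Butterfly | -1.42 (-5.98, 3.14) | -3.52 (-5.05, -1.99) | -3.58 |
| Left molar inclination, MSE-Butterfly | -0.66 (-4.74, 3.42) | -2.89 (-4.70, -1.08) | -2.69 |
| Incisor inclination, MSE-Butterfly | +0.17 (-3.97, 4.31) | -2.44 (-4.08, -0.80) | -2.57 |
| Hard palate width 6, MSE-Butterfly | +0.72 (-1.28, 2.72) | +2.27 (1.33, 3.20) | +2.74 |
| Molar distance, MSE-Butterfly | +1.58 (-0.68, 3.84) | +2.53 (1.45, 3.62) | +3.00 |
| Hard palate width 4, MSE-Hybrid | +1.03 (-0.38, 2.44) | +1.18 (0.20, 2.16) | +1.26 |

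Overall ANCOVA p for the first three rows: .000002, .0006 and .002. The last two rows share a letter on post values in the tables but not on change; their Bonferroni p after adjustment is <.0001 and .013. Separate slopes by arm leave the first four rows at -3.57, -2.82, -2.35 and +2.13, all with intervals excluding zero.

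**Precision.** In the first four rows ANCOVA residual variance is 11%, 19%, 15% and 20% of post-only. Against change it is 1.02, 0.99, 1.01 and 0.72. Over the 13 measures it is clearly below change in four (molar distance 0.56, hard palate width 6 0.72, nasal floor premolar and hard palate width 4 about 0.79) and within 5% in nine.

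**Molar distance, MSE minus Hybrid.** The pooled slope is 0.676 and Hybrid starts 44.79 - 42.14 = 2.65 higher. Adjusted difference = (51.01 - 52.21) + 0.676 × 2.65 = -1.20 + 1.79 = +0.59; SE 0.451; interval -0.53 to 1.72; Bonferroni p=.59. ANOVA on change, standing in for the rank test, gives +1.46 (0.04, 2.88), p=.042.
- Arm slopes are 1.00/0.60/0.69 (Butterfly/Hybrid/MSE), heterogeneity p=.073, and the Hybrid implied correlation is 0.986. At the Hybrid, MSE and Butterfly slopes the pair gives +0.38 (p=1), +0.63 (p=.42) and +1.45 (p=.044). Separate slopes at the mean pre value give +0.51 (-0.58, 1.60).
- With 7.24 in place of 7.42 for Hybrid change, ANCOVA gives +0.71 to +0.77 (p=.28-.37) and change +1.64 (p=.019).
- Data simulated to the printed change moments give a Mann-Whitney p times 3 with median .085 (5-95% range .041-.166) if normal and .056 (.006-.357) if exponential-shaped. Both shapes are assumptions.

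**The case against.** The strongest reply is that the SAP already tests change and reports it, so adjustment alters little. Much of this stands. The overall ANCOVA verdict agrees with change in 13 of 13 measures, and 37 of 39 pairs stay on the same side of .05 when ANOVA on change is the comparator. One of the two crossings, incisor inclination MSE-Hybrid (.041 to .059), is marginal. The large contrast is with raw post values only. It remains that the post results are reported as between-group comparisons with nothing to say they should give way.

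A second reply is that the rebuilt ANCOVA rests on SDs from tables that contain impossible entries. That also stands as a limit. The three overall results need the high implied correlations (0.84 to 0.97 across arms); at an assumed r=0.7 in every arm the overall p-values would be .09, .14 and .35.

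A reader might go further and infer that the raw comparisons are biased, or that the missing covariate makes the MSE-over-Hybrid result on molar distance wrong. The documents support neither. Randomisation protects both raw contrasts. For molar distance the results text states only an overall difference and an order, and ANCOVA keeps that order (MSE, Hybrid, Butterfly); the pairwise claim is in the table letters. The test behind those letters is not named and may be fragile before any adjustment, and an interval of -0.53 to 1.72 does not show equality.

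**Conclusion.** The point holds, at a level that should be fixed but does not overturn the overall results. Three overall post results and at least three pairwise post results read as no difference only because the pre value is ignored. The pairwise count is a minimum: only hard palate width 6 is stated in prose, and the other two come from the table letters. Nasal floor molar shows the same conflict (post p=.397, change p=.000), but its printed SDs do not allow a check.

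The gain over raw change is real in four measures (21-44% less residual variance) and negligible in the other nine usable ones. MSE over Hybrid on molar distance should be treated as uncertain until checked on patient data: the estimate moves from +1.46 on change to +0.59 adjusted, the Hybrid row is unusual, and the slopes may differ between arms. All adjusted figures assume that the printed SDs in the rows used are right and, unless stated otherwise, a common slope.

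**What to change.** 1. Before refitting, verify the inputs against patient data: the Butterfly SDs for premolar distance, nasal floor molar and arch depth; the left premolar inclination change SDs; the Hybrid molar-distance change (7.24 in the text, 7.42 in Table 1); and the hard palate width 6 changes, given in the text as "Butterfly hydrax ( $3.37 \pm 0.96$ ) and Hybrid hyrax ( $3.17 \pm 1.54" but the other way round in Table 2.
2. For each of the 17 outcomes with baseline variation, fit post value on group plus pre value, with Bonferroni-adjusted pairwise 95% CIs. Add a small-sample robust SE (for example HC3) as a sensitivity analysis. State beforehand that, if slopes differ, contrasts from a separate-slopes model at the overall mean pre value are also reported.
3. Label this analysis post hoc, report it beside the Kruskal-Wallis test on change, and name the pairwise test behind the change letters.
4. Draw no between-group conclusions from unadjusted post values. Report MSE over Hybrid on molar distance as dependent on the method.

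Reconcile as separate items, which do not add to the weight of this point:
- The direction of change for molar and premolar inclination. The text says of each that "The mean value of amount of change (difference) recorded in MSE was significantly higher than that recorded in Butterfly hydrax and Hybrid hyrax", whereas Table 2 shows MSE lowest (right molar: 2.08 against 5.66 and 4.85).
- The ordering of Butterfly and Hybrid for posterior suture opening, text against Table 3.
- The incisor post p-value, .922 in the text and .992 in Table 3.

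The cost is a data check, a few lines of SAP text and one linear model per outcome on data in hand. The downside is that the tables must be rerun and the adjusted results carry a post hoc label, because the results are already known.

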	Hybrid hyrax	76.99	6.07	78.65	5.55	1.65	2.50	1.10	.000*
	MSE	75.14	5.83	76.16	5.95	1.02	.47	1.10	.000*
	P value bet. groups	.455ns		.283ns		.410ns			

Significance level p≤0.05, \*significant, ns=non-significant

Post hoc test: Within the same comparison, means sharing the same superscript letter are not significantly different

Table (2) Descriptive statistics and comparison between (ANOVA test) and within group (i.e. between pre and post value) (paired t test) regarding nasal floor, hard palate maxillary width molar and premolar; molar and premolar inclination right and left

GROUP	Pre		Post		Amount of change (post-pre)			P Within group	
	Mean	Std. Dev	Mean	Std. Dev	Mean	Std. Dev	Median		
Nasal floor 1 st .molar	Butterfly hyrax	65.13	5.07	67.33	1.67	2.20 b	1.49	1.80	.003*
	Hybrid hyrax	63.48	3.13	66.08	2.80	2.60 b	1.04	2.40	.000*
	MSE	62.00	3.36	66.38	3.07	4.38 a	.85	4.45	.000*
	P value bet. groups	.058ns		.397ns		.000*			
Nasal floor 1 st .premolar	Butterfly hyrax	34.57	1.55	37.04 c	1.17	2.47 c	1.02	2.40	.001*
	Hybrid hyrax	35.21	2.09	38.63 b	1.77	3.43 b	.74	3.50	.000*
	MSE	34.86	2.40	39.73 a	2.27	4.87 a	.62	5.00	.000*
		.701ns		.001*		.000*			
Hard palate Maxillary width 6	Butterfly hyrax	60.43	2.49	63.59 ab	2.15	3.17 b	1.54	3.10	.000*
	Hybrid hyrax	58.67	2.99	62.04 b	2.68	3.37 b	.96	3.40	.000*
	MSE	58.39	2.44	64.31 a	1.80	5.91 a	.92	6.10	.000*
	P value bet. groups	.083ns		.023*		.000*			
Hard palate Maxillary width 4	Butterfly hyrax	33.66	1.85	38.17 b	1.76	4.51 b	1.28	4.50	.001*
	Hybrid hyrax	34.22	1.79	39.31 ab	1.39	5.09 b	1.16	4.90	.001*
	MSE	33.99	1.58	40.34 a	1.56	6.35 a	1.25	6.10	.003*
	P value bet. groups	.677ns		.002*		.001*			
Right.1 st molar inclination	Butterfly hyrax	18.58	4.41	24.24	5.32	5.66 a	1.52	5.80	.000*
	Hybrid hyrax	18.43	5.33	23.27	5.20	4.85 a	2.10	6.00	.000*
	MSE	20.74	5.06	22.82	4.77	2.08 b	1.30	1.70	.000*
	P value bet. groups	.353ns		.734ns		.000*			
Left.1 st molar inclination	Butterfly hyrax	18.45	4.34	23.67	6.07	5.21 a	2.74	6.30	.000*
	Hybrid hyrax	19.09	3.08	23.71	3.68	4.62 a	1.62	4.90	.000*
	MSE	20.49	3.78	23.01	3.53	2.52 b	1.31	2.35	.000*
	P value bet. groups	.312ns		.892ns		.003*			

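### The SAP names no post hoc test after Kruskal-Wallis for the change scores, yet the outcome tables carry pairwise letters that fit a pooled-variance parametric test; several are borderline and may not survive a rank-based follow-up

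*SAP*

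**What the plan says.** The SAP section Statistical analysis gives two routes. Normally distributed variables are compared between groups by "ANOVA test followed by Bonferroni post hoc test whenever a significance difference was detected". The change scores (after minus before) are treated separately: "Difference data were non-parametric and were compared between groups using Kruskal Wallis test". No pairwise procedure is attached to that second route. The section adds "All p-values are two-sided" and sets significance at .05.

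The captions of the outcome Tables 1 to 3 read "Descriptive statistics and comparison between (ANOVA test) and within group", with the paired t test for the within-group part. Kruskal-Wallis does not appear in them. The Amount of change column carries superscript letters, explained only by "Post hoc test: Within the same comparison, means sharing the same superscript letter are not significantly different". The Results text (II- Outcomes) turns these letters into pairwise statements about change for most outcomes.

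**The concern.** A reader cannot tell which test produced the pairwise verdicts on change. If the plan is read literally, the only available post hoc test belongs to data that the SAP says these are not. The caption then attributes the whole column to ANOVA.

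This affects conclusions as well as labels. The three-tier result for molar distance, the first outcome reported (Butterfly c, Hybrid b, MSE a), and the Hybrid against MSE verdict for premolar distance both rest on pairwise p-values close to .05. For such pairs the choice of test can decide whether a difference is reported.

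**Working it through.** **Inputs.** Means, SDs and medians of change come from the outcome Tables 1 to 3. Group sizes are 15, 15 and 16 (Butterfly, Hybrid, MSE), from the demographic Table 2. For Hybrid molar distance I use the table's 7.42, which equals post minus pre (52.21 − 44.79); the text prints 7.24. Three mean changes are missing from Table 3 as read, so I took post minus pre: arch depth MSE 23.38 − 24.72 = −1.34; incisor inclination Butterfly 114.46 − 117.31 = −2.85 and MSE 114.63 − 120.05 = −5.42.

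**Step 1: are the overall p-values ANOVA?** F = (between-group SS / 2) / (within-group SS / 43). The last column lets every mean and SD vary by ±.005.

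| Change in | F | ANOVA p | Printed p | ANOVA p with rounding |
|---|---|---|---|---|
| Right molar rotation | (0.446/2)/0.403 = 0.553 | .579 | .503 | .544 to .614 |
| Premolar distance | (42.38/2)/3.348 = 6.33 | .0039 | .005 | .0036 to .0042 |
| Left molar inclination | (62.46/2)/3.897 = 8.01 | .0011 | .003 | .0010 to .0012 |

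Rounding does not close these gaps. The values are compatible with Kruskal-Wallis, as Statistical analysis says, so the caption is wrong for this column.

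**Step 2: which test gives the letters?** Pooled variance s² = Σ(nᵢ − 1)sᵢ² / 43; SE = s√(1/nᵢ + 1/nⱼ); p from t on 43 df, times 3 for Bonferroni.

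Molar distance: s² = (14 × 1.39² + 14 × 1.77² + 15 × 1.58²)/43 = 108.36/43 = 2.520, so s = 1.587.
- Butterfly-Hybrid: t = 1.54/0.580 = 2.66, p = .011, × 3 = .033.
- Hybrid-MSE: t = 1.46/0.5705 = 2.56, p = .0141, × 3 = .042.

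Both are significant, which reproduces c/b/a. Other rows, pooled Bonferroni:

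| Change in | Butterfly-Hybrid | Butterfly-MSE | Hybrid-MSE | Printed letters |
|---|---|---|---|---|
| Premolar distance | 1.0 | .004 | .048 | a/a/b |
| Nasal floor premolar | .007 | <.001 | <.001 | c/b/a |
| Hard palate width 4 | .61 | <.001 | .020 | b/b/a |
| Left molar inclination | 1.0 | .001 | .015 | a/a/b |
| Right premolar inclination | <.001 | <.001 | .196 | a/b/b |
| Incisor inclination | .46 | <.001 | .042 | incomplete; text agrees |
| Arch depth | .58 | .001 | <.001 | incomplete; text agrees |

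Of 12 complete letter sets on change, 11 match. The exception, left premolar inclination, cannot be checked because its printed SDs repeat the means. Tukey and unadjusted LSD give the same letters as Bonferroni.

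**Step 3: how firm are the verdicts?** Welch drops the pooled SD: SE = √(sᵢ²/nᵢ + sⱼ²/nⱼ), again × 3. All three pairs are Hybrid-MSE.

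| Change in | Pooled Bonferroni | Welch t (df) | Welch p | Welch × 3 |
|---|---|---|---|---|
| Molar distance | .042 | 1.46/0.604 = 2.42 (28.1) | .0224 | .067 |
| Premolar distance | .048 | 1.65/0.658 = 2.51 (28.8) | .0180 | .054 |
| Right premolar inclination | .196 | 0.95/0.283 = 3.35 (20.8) | .0030 | .009 |

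For premolar distance the SDs are nearly equal (1.83, 1.84, 1.82), so the shift comes from losing the 43 pooled df. For right premolar inclination the SDs are 2.18, .98 and .51, and the pooled SD is driven by Butterfly.

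**Step 4: rank-based follow-up.** This needs patient data, which the documents do not contain. As a guide under assumptions, data sets were simulated to the printed means and SDs with normal and skewed shapes, and also to the printed medians. Share in which the pair is significant, across shapes:

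| Pair | Dunn-Bonferroni | Mann-Whitney-Bonferroni |
|---|---|---|
| Molar distance, Butterfly-Hybrid | 7–29% | 43–79% |
| Molar distance, Hybrid-MSE | 1–18% | 11–60% |
| Premolar distance, Hybrid-MSE | 8–56% | 8–66% |
| Nasal floor premolar, Butterfly-Hybrid | 0–6% | 91–98% |
| Right premolar inclination, Hybrid-MSE (printed as not different) | 9–35% | 97–100% |

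No rank procedure tried reproduced all the printed letters.

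**The case against.** The strongest reply is that this is a reporting gap, and that going further means arguing from invented data. Much of that stands.

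A reader might infer that a rank-based follow-up overturns the printed rankings. The documents do not support that. Losing significance does not reverse an order, and the printed medians keep the order of the means in the disputed rows (molar distance 5.77, 7.50, 8.95; premolar distance 6.20, 5.90, 4.85; nasal floor premolar 2.40, 3.50, 5.00). The simulated shares are wide and depend on the procedure: nasal floor premolar usually falls with Dunn and stays with Mann-Whitney, and the extra difference in right premolar inclination appears reliably only with Mann-Whitney. Multiplicity adjustment matters too. In the median-matched simulations without adjustment, molar distance Hybrid-MSE was significant in 66% (Dunn) and 96% (Mann-Whitney). The SAP specifies no adjustment after Kruskal-Wallis.

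A reader might also conclude that the letters are Bonferroni letters. That is only an inference from its being the one post hoc test named, since Tukey and LSD fit as well.

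What the reply does not remove is the gap itself, the caption that Step 1 contradicts, and the Welch results, which come from the printed tables without simulation.

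**Conclusion.** The point holds as a should-fix. The SAP has no post hoc test for the analysis it assigns to change. The overall p-values in that column are not all ANOVA, contrary to the captions, and the letters fit a normal-theory, equal-variance test that the SAP does not assign to these data.

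What is at stake is a handful of adjacent pairs: molar distance (both adjacent pairs), premolar and incisor Hybrid-MSE, and possibly nasal floor premolar Butterfly-Hybrid could lose significance, while right premolar inclination Hybrid-MSE could gain it. The MSE against Butterfly differences marked significant are not in doubt: they held in 71 to 100% of simulated data sets with Dunn-Bonferroni, leaving aside left premolar inclination. No replacement ranking can be stated from the documents.

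This rests on the tabled summaries being correct and on 15/15/16 patients in every row. If the text's 7.24 were the right Hybrid molar change, Butterfly-Hybrid would be t = 1.36/0.580 = 2.35, adjusted p about .07.

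**What to change.** In SAP, Statistical analysis, add after the Kruskal-Wallis sentence one multiplicity-adjusted rank follow-up, for example Dunn with Bonferroni, or pairwise Mann-Whitney with Bonferroni for three comparisons. Choose it on method, without regard to which letters it yields, and state that it was specified after the results were known. Then:

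- rerun it on the raw change scores for every outcome;
- reissue the Amount of change letters in the outcome Tables 1 to 3 and the pairwise sentences on change in Results, II- Outcomes, with whatever results;
- name Kruskal-Wallis and the follow-up test in the captions for that column, keeping ANOVA for the pre and post columns;
- correct the left premolar inclination SDs and settle 7.24 against 7.42 while the tables are open.

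The cost is one SPSS rerun and some rewording. The downside is that a few borderline differences may lose significance.
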